### 7.1.4 Significant Non-Serious Adverse Events

A significant non-serious adverse event is an AE that does not meet the serious criteria, is considered significant by the Sponsor, and requires expedited reporting. These events include:

- Peripheral non-progressive non-infectious corneal ulcers;
- All symptomatic corneal infiltrative events;
- All cases of corneal staining greater than or equal to Grade 3:
- A temporary loss of two or more lines of BSCVA (for greater than or equal to 2 weeks);
- Neovascularization cases Grade 2 or greater;
- Any ocular event that necessitates temporary lens discontinuation of greater than or equal to 2 weeks.

### 7.1.5 Non-Significant Non-Serious Adverse Events

A non-significant non-serious adverse event may include but are not limited to the following and does not require expedited reporting:

- Bacterial Conjunctivitis:
- Viral Conjunctivitis:
- Allergic Conjunctivitis;
- Corneal Edema;
- Contact Lens Related Papillary Conjunctivitis; and,
- Loss of Contrast Sensitivity

## 7.2 Adverse Event Treatment and Culturing

With any AE, treat the subject as appropriate to prevent further complications and to potentially resolve the event consistent with the standard of care.

For purposes of this study, the Sponsor requests that cultures should be obtained in cases of corneal ulcer or suspected ocular infection, unless medically contraindicated. Cultures should be taken from the cul-de-sac, lower eyelid margin, and the corneal lesion (if applicable). The required culturing techniques are outlined in APPENDIX D:.

When a culture is obtained, the contact lenses and contact lens cases which were being utilized by the subject at the time of the AE should be collected from the subject for culturing and processing by the local clinical laboratory designated by the site.

Microbial data generated from returned subject supplies (e.g. lenses, lens cases, and/or lens case solutions) are for information only. Because microbes may be introduced into subject supplies during use, recovery of microbes from returned subject supplies cannot be presumed to indicate etiology or direction of organism transmission.

The ocular cultures, along with the associated contact lenses and contact lens cases, will be sent to the local clinical laboratory designated by the site for analysis. The clinical laboratory will report the culture results to the Investigator who will record the results in the eCRF.

#### 7.3 Evaluations

When evaluating for reportable AEs, the Investigator must first determine if the event is serious (refer to Section 7.1.3 for criteria) and/or significant (refer to Sections 7.1.4 and 7.1.5) and then assess the severity of symptoms and the relationship of the event to the study device using the following guidelines:

### 7.3.1 Severity

- **Mild:** Subject awareness of a sign or symptom that is easily tolerated, requires no treatment, and does not interfere with subject's daily activities.
- Moderate: Subject awareness of a sign or symptom which may be a low level of concern to the subject and may interfere with daily activities but can be relieved by simple therapeutic care.
- **Severe:** A sign or symptom that interrupts the subject's daily activity and requires systemic therapy or other treatment

### 7.3.2 Relationship to Study Device and/or Rewetting Drops

- **Related:** There is at least a reasonable possibility that the AE is related to the study device (study solution) and/or rewetting drops. Reasonable possibility means that there is evidence to suggest a causal relationship or association between the study device and/or rewetting drops and the AE. Also referred to as an ADE.
- **Not related:** There is little or no reasonable possibility that the AE is related to the study device (study solution) and/or rewetting drops. This assessment implies that the AE has no evidence to suggest either a causal relationship or association to the study device and/or rewetting drops and a more likely or certain alternative etiology exists.

#### 7.4 Procedures for Reporting SAEs and Significant Non-Serious Adverse Events

An AE classified as a SAE or a Significant Non-Serious AE requires expeditious handling and reporting to the Sponsor to comply with regulatory requirements, as follows:

The event must be reported to the Medical Monitor (or designee) within 24 hours of the Investigator's awareness of the event via facsimile/email transmission on a paper SAE or Significant Non-Serious AE Report Form signed by the Investigator.

The Medical Monitor (or designee) will email a copy of the form (within 24 hours) to

- Investigators should not wait to receive additional information to fully document the event before initially notifying the Medical Monitor of an SAE or a Significant Non-Serious AE. Additional relevant information such as hospital records and autopsy reports should be provided to the Medical Monitor as soon as they are available.
- The Investigator should take all appropriate measures to ensure the safety of the subjects: notably, he/she should follow a subject with an SAE or Significant Non-Serious AE until the event has resolved or the condition has stabilized. This may imply that follow-up will continue after the subject has left the study, and that additional evaluations may be requested by the Sponsor.
- Ensure that the subject's identity is protected and the subject's identifiers in the clinical trial are properly mentioned on the form.
- BEGIN TREATMENT OF THE AE IMMEDIATELY BY A SUITABLY LICENSED EYE CARE PROFESSIONAL.
- Continue to update the paper SAE or Significant Non-Serious AE Report Form, if applicable, each time the subject is seen during the management of the event and at resolution of the event. All updated report forms should be submitted to the Medical Monitor who will distribute the reports as stated above. Whenever possible, it is suggested that the Investigator take photographs of all applicable AEs and forward them to the Medical Monitor.
- Events requiring medical treatment will be evaluated by the Sponsor. Upon review of the medical treatment, Bausch + Lomb Clinical Operations representatives may contact the Investigator to request further information concerning the treatment.

- Report all UADEs to the reviewing IRB within 10 working days following awareness of the UADE or according to the established reporting procedures of the IRB, whichever is shorter.
- Submit all bills, prescription receipts, and culture reports/fees related to the AE to the Bausch + Lomb Clinical Operations. Expense incurred for study related medical treatment will be paid by Bausch +Lomb Clinical Operations.
- Full details of the process for reporting adverse events are outlined in the Safety Management Plan.

# 7.4.1 Off-Site Unanticipated Serious Adverse Device Effect Reporting

When participating in multicenter clinical investigations, Investigators may receive offsite UADE reports. These are Sponsor reports of UADEs which occurred at other clinical sites for the same trial, or in different trials using the same test article, that met the criteria for reporting to a regulatory agency. These should be reported to the reviewing IRB within 10 working days or per their established reporting procedures, whichever is shorter.

# 7.4.2 Reporting Device Deficiencies

A device deficiency is defined as an inadequacy of a medical device with respect to its identity, quality, durability, reliability, safety, or performance. Device deficiencies include malfunctions, use errors, and inadequate labeling.

Investigators must evaluate, record, and report via applicable forms any complaints/ deficiencies or malfunctions experienced with the study solution during this trial to the Medical Monitor promptly. The Sponsor and Medical Monitor shall review all device deficiencies, and, upon the Sponsor's request, Investigators must supply any additional information related to the safety reporting of a particular event.

Report device deficiencies within 24 hours of knowledge to:

The Medical Monitor will distribute, within 24 hours of knowledge, all device deficiencies to the Sponsor including:

The Sponsor shall review all device deficiencies and determine and document in writing whether they could have led to an SAE. In the event of a disagreement between the Sponsor and the Investigator(s), the Sponsor shall communicate both opinions to the reviewing IRB per their established reporting procedures and the health authority.

#### 7.4.3 Guidelines for Reporting Pregnancies

All female subjects of childbearing potential must use an effective method of birth control during the study, to include 2 weeks after last visit, in a manner such that risk of contraceptive failure is minimized. Abstinence is allowed as a birth control method.

During the study, all female subjects of childbearing potential should be instructed to contact the Investigator immediately if they suspect they might be pregnant (e.g. missed or late menstrual period). Female subjects who become pregnant during the study will be followed until completion of pregnancy. Every effort will be made to obtain the health status of the mother and infant or fetus (in cases of miscarriage or therapeutic abortion) at term. Pregnancy itself is not considered an AE.

All confirmed pregnancies must be reported on a paper Pregnancy Report Form and submitted to the Medical Monitor via facsimile or email transmission within 24 hours of the Investigator's awareness of the pregnancy. The Medical Monitor will distribute the completed form to the Sponsor as per the distribution list in Section 7.4.

All pregnancies will be followed until outcome even after study closure. The outcome of all pregnancies will be reported on a paper Pregnancy Outcome Report Form and submitted to the Medical Monitor via facsimile or email transmission once the outcome is learned. The Medical Monitor will distribute the completed form to the Sponsor as per the distribution list in Section 7.4.

Although pregnancy occurring in a clinical study is not considered to be an AE or SAE, any pregnancy complication, spontaneous abortion, or elective termination of a pregnancy, for medical reasons, will be recorded as an SAE. Any serious complication or event resulting from the pregnancy should be reported to the Medical Monitor within 24 hours on the SAE or Significant Non-Serious AE Report Form along with the Pregnancy Report Form.

The contact for reporting pregnancies and pregnancy outcomes is:

#### 8.0 STATISTICAL METHODS

#### 8.1 Study Endpoints

- **8.1.1** Primary Safety Endpoint
  - Slit lamp findings greater than grade 2
- **8.1.2** Primary Effectiveness Endpoints
  - Overall comfort at all scheduled follow-up visits
  - Dryness at all scheduled follow-up visits

#### **8.1.3** Secondary Effectiveness Endpoints

There are no secondary effectiveness endpoints.

#### 8.2 Hypotheses

#### **8.2.1** Slit Lamp Findings

The null hypothesis  $(H_0)$  is that the difference in the proportion of eyes with slit lamp findings greater than grade 2 (test group proportion  $[\pi_T]$  minus standard group proportion

 $[\pi_S]$ ) is greater than or equal to 0.05 (5%). The alternative hypothesis  $(H_1)$  is that the difference is less than 0.05 (5%).

$$H_0: \pi_T - \pi_S \ge 0.05$$

$$H_1$$
:  $\pi_T - \pi_S < 0.05$ 

#### **8.2.2** Overall Comfort

The null hypothesis  $(H_0)$  is that the difference in mean overall comfort (test group mean  $[\mu_T]$  minus standard group mean  $[\mu_S]$ ) is less than or equal to negative five points. The alternative hypothesis  $(H_1)$  is that the difference is greater than negative five points.

$$H_0: \mu_T - \mu_S \le -5$$

$$H_1: \mu_T - \mu_S > -5$$

#### **8.2.3** Dryness

The null hypothesis  $(H_0)$  is that the difference in mean dryness score (test group mean  $[\mu_T]$  minus standard group mean  $[\mu_S]$ ) is less than or equal to negative five points. The alternative hypothesis  $(H_1)$  is that the difference is greater than negative five points.

$$H_0: \mu_T - \mu_S \le -5$$

$$H_1: \mu_T - \mu_S > -5$$

# 8.3 Sample Size

Estimates of standard deviations and proportions were obtained from Bausch + Lomb Study #872.

The sample size calculations assume that the level of analysis will be the eye and that the outcomes from each subject's eyes will be independent. This is a standard assumption for contact lens care product trials.

The recommended minimum sample size is 20 Test group subjects per lens stratum. Therefore, with eight strata the targeted completed sample size will be (20 Test subjects/stratum + 20 Control subjects/stratum) x 8 strata = 320 subjects (assuming sufficient statistical power is provided by this sample size).

Sample size calculations were completed using nQuery Advisor® 7.0 software.

#### **8.3.1** Slit Lamp Findings

In Study 872, the proportion of eyes with slit lamp finding greater than grade 2 at any follow up visits was 0.005. With 320 eyes (160 subjects) in each group, the upper limit of the observed one-sided 95% confidence interval will be expected to be less than 0.05 with 99% power when the Standard proportion,  $\pi_S$ , is 0.005 and the Test expected proportion,  $\pi_T$ , is 0.005. Results are based on 100,000 simulations using the Newcombe-Wilson score method to construct the confidence interval.

#### **8.3.2** Overall Comfort

In Study 872, the standard deviation of overall comfort ratings averaged over all visits was 13.9 units. When the sample size in each group is 320 eyes (160 subjects), a two group 0.05 one-sided t-test will have 99% power to reject the null hypothesis that the test

is not non-inferior to the control (the difference in means,  $\mu_T$  -  $\mu_S$ , is -5 or farther from zero in the same direction) in favor of the alternative hypothesis that the test is non-inferior, assuming that the expected difference in means is 0 and the common standard deviation is 13.9.

#### **8.3.3** Dryness

In Study 872, the standard deviation of dryness ratings averaged over all visits was 13.9 units. When the sample size in each group is 320 eyes (160 subjects), a two group 0.05 one-sided t-test will have 99% power to reject the null hypothesis that the test is not non-inferior to the control (the difference in means,  $\mu_T$  -  $\mu_S$ , is -5 or farther from zero in the same direction) in favor of the alternative hypothesis that the test is non-inferior, assuming that the expected difference in means is 0 and the common standard deviation is 13.9.

#### **8.3.4** Overall Power

If the primary endpoints are independent, the overall power of the study is  $99\% \times 99\% \times 99\% = 97\%$ .

# **8.3.5** Enrollment Target

The desired completed sample size is 160 subjects per group. Allowing for up to 13% losses, the enrollment target in each treatment group will be approximately  $[160 \div (1 - 0.13)] = 184$  subjects. The total enrollment target will be approximately 2 x 184 = 368 subjects (736 eyes).

#### 8.4 Randomization

Subjects will be randomized to one of two treatment arms in a 1:1 ratio, using Test drops or Control drops for the duration of the study. Randomization will be managed using ORS. The randomization will be stratified by lens group within investigational site. The lens group will be determined by the subjects' habitual lens material at Screening/Dispensing and will be one of the groups shown in Table 1: Lens Groups (page 13).

Efforts will be made to enroll subjects in at least four of the lens strata within each site to minimize confounding between site and lens strata. It should be noted that while the target enrollment for each lens strata is approximately 40 subjects (approximately 20 per treatment arm), some lens strata may be difficult to enroll.

An unmasked statistician who is not otherwise involved in the trial will create the randomization schedule.

#### 8.5 Study Populations

#### **8.5.1** Intent-to-Treat (ITT) Population

The ITT Population will consist of all randomized subjects and both of their eyes. Subjects will be included in ITT Population summaries according to the treatment group to which they were randomly assigned.

#### **8.5.2** Per Protocol (PP) Population

The PP population will be the primary population used for analysis of the primary effectiveness endpoints. The PP Population will consist of all ITT Population subjects without important (major) protocol deviations for subject level summaries and, for eye level summaries, both of their eyes. Important protocol deviation categories are defined in Section 8.6.4. Subjects will be included in PP Population summaries according to the treatment group to which they were randomly assigned. Membership in the PP population will be determined prior to study unmasking.

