## 3.2.3 Subject Discontinuation

A subject MAY be discontinued (at the discretion of the Investigator, the Sponsor, and/or the IRB) prior to the final study visit for a variety of reasons, including, but not limited to:

- An adverse event (AE) occurring during the course of the study, which precludes continued treatment or follow-up
- Persistent Grade 3 or 4 slit lamp findings (must be reported to the Sponsor within 24 hours)
- Persistent study-related symptoms/complaints

A subject MUST be discontinued prior to the final study visit (1-Month Visit [Visit 3]) for any of the following reasons:

- Voluntary withdrawal
- Death
- Investigator decision that it is not in the best medical interest of the subject to continue participation in the investigation
- Ineligible at screening/dispensing a subject who was enrolled but was later found to have not met the eligibility criteria
- Inability to maintain recommended wearing and rewetting drop schedule
- Continued failure to follow subject instructions
- Lack of motivation
- Lost to follow-up (refer to Section 3.2.4)
- Instillation of non-medically indicated solution not specified in the protocol
- Other eve is discontinued
- Becomes pregnant during the study

Prior to discontinuing a subject, every effort should be made to contact the subject, schedule an Exit Visit, obtain as much follow-up data as possible, and retrieve all study materials. Adverse events will be followed as described in Section 7.0. Subject discontinuations will be documented clearly on the source document and applicable electronic case report form (eCRF). The Investigator should indicate the PRIMARY (one) reason that the subject was discontinued for each eye. Subjects who are discontinued from the study following randomization will not be replaced.

Exit Visit assessments should be completed for discontinued subjects.

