#### 8.6.1.3 Overall Comfort

At each follow-up visit, overall comfort will be assessed for each eye on a scale from 0 to 100, with 100 denoting the most favorable response. For each eye, mean overall comfort

over all follow-up visits will be computed as the average of the non-missing values over all scheduled follow-up visits. Missing data will not be imputed for the primary analysis. Mean overall comfort over all follow-up visits will be summarized at the eye level by treatment using continuous summary statistics for the Per Protocol Set in a table. A one-sided lower 95% confidence limit around the difference in means between the test and control treatment groups, computed using an analysis of variance model including the fixed factor of treatment and the fixed blocking factor of site, will be displayed. If the lower confidence limit is greater than -5, then the null hypothesis that the test solution is not non- inferior will be rejected, and the test solution will be statistically successful in this outcome.

As a sensitivity analysis, the ITT Population will be analyzed for this endpoint. Summaries by treatment and a confidence interval around the difference in means will be provided as described above using the available data. Twenty imputations of missing overall comfort data will be produced by treatment group using the Markov chain Monte Carlo (MCMC) method. The variables used to create the imputed datasets will be the overall comfort scores observed at each scheduled visit. The differences and standard errors estimated by imputation will be combined to create an estimated difference and confidence limit.

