#### **8.6.4** Protocol Deviations

Important (major) protocol deviations will be summarized by category and treatment group for the ITT Population in a table.

Categories of important protocol deviations will include the following, which will be derived via data entered on the case report forms.

- Ineligibility
- Not dispensed study treatment
- Mis-randomization
- Dispensing of the incorrect study treatment
- Dispensing and use of lenses from the incorrect lens group
- Use of medications that could potentially affect any of the primary effectiveness endpoints

• Failure to comply with the procedures used to assess the primary effectiveness endpoints, such as missing the scheduled visit or failing to complete the procedure in accordance with instructions

Additional important protocol deviation categories may be added prior to unmasking. Important (major) protocol deviations will also be displayed in a listing.

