# **8.6.7** Missing Data

Imputation of missing data is not conservative in a non-inferiority analysis setting. Therefore, primary effectiveness analyses will be completed using the PP Set without imputation of missing data.

Sensitivity analyses of data from the ITT Set with missing data imputation are described in Section 8.6.1. Unless otherwise specified in the protocol or statistical analysis plan, missing data will not be imputed.

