# **8.6.8** Multiple Comparisons

Statistical success depends on success for all primary endpoints. Therefore, adjustments for multiple comparisons are not necessary.

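### Success on comfort and dryness is decided in the Per Protocol set alone, and the plan gives no consequence if the ITT analysis disagrees

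*Combined protocol and SAP*

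**What the plan says.** Section 8.5.2 makes PP primary for effectiveness: "The PP population will be the primary population used for analysis of the primary effectiveness endpoints". It defines the set by exclusion: "The PP Population will consist of all ITT Population subjects without important (major) protocol deviations". Membership is fixed before unmasking.

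The important deviations are listed in 8.6.4. Most are administrative (ineligibility, mis-randomisation, wrong product, wrong lens group). Two are not: use of medications that could affect the primary effectiveness endpoints, and "Failure to comply with the procedures used to assess the primary effectiveness endpoints, such as missing the scheduled visit".

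Section 8.6.1.3 averages each eye's non-missing ratings over the scheduled follow-up visits. It declares success if the one-sided 95% lower limit for Test minus Control, in the PP set, is above -5. Section 8.6.1.4 uses the same methods for dryness. On the other set, 8.6.1.3 says: "As a sensitivity analysis, the ITT Population will be analyzed for this endpoint". That analysis uses the available data and also 20 MCMC imputations, but no criterion is attached to either.

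Section 8.6.7 first states that imputation is not conservative in a non-inferiority setting and then concludes: "Therefore, primary effectiveness analyses will be completed using the PP Set without imputation of missing data". Section 8.6.8 gives the overall rule: "Statistical success depends on success for all primary endpoints". It does not refer to ITT.

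**The concern.** A subject who tolerates the drop poorly may stop coming, or may need a medication that could affect the endpoints. Either event can take the subject out of PP. Section 3.2.3 allows discontinuation for "Persistent study-related symptoms/complaints" and requires it for, among other reasons, "Inability to maintain recommended wearing and rewetting drop schedule". If such a subject gave a poor 2-Week rating and is then excluded from PP, a rating that was observed under randomised treatment does not count towards the verdict. ITT would keep it, but ITT cannot change the verdict.

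If this happens more often on Test than on Control, the PP difference moves towards zero and the 5% error rate is no longer held for the randomised population. Fixing PP membership before unmasking prevents selection by the analyst. It does not prevent selection by the subject's own experience, and section 4.7 concedes that the two products' containers look different.

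Section 8.6.7 does not close the gap. It treats two separate choices as one. Whether to impute is one question, and which observed ratings to use is another. An ITT analysis on available ratings needs no imputation and is already planned in 8.6.1.3.

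**Working it through.** **Inputs from the plan.** SD 13.9 and 160 subjects (320 eyes) per group (8.3.2, 8.3.3); margin 5 and one-sided alpha 0.05 (Synopsis, 8.2.2, 8.2.3); 184 enrolled per group with up to 13% losses (8.3.5).

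**The plan's own figures.** Standard error of the difference = 13.9 × √(2/n).
- Eye level: 13.9 × √(2/320) = 1.10. Power at a true difference of 0 is 99.8% (noncentral t), in line with the stated 99%.
- Subject level: 13.9 × √(2/160) = 1.55. Power is 94.1% (noncentral t) or 94.2% (normal approximation).
- Enrolment: 160 ÷ 0.87 = 184. Overall power: 0.99³ = 0.97. Both reproduce.

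The eye level is the plan's assumption that a subject's two eyes are independent. The subject level is the other bound, with the two eyes carrying the information of one.

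**False success in PP.** Suppose the true all-randomised difference is exactly -5, on the boundary of the null hypothesis. Suppose also that a fraction *e* of the Test arm, over and above any similar removal on Control, is rated and then excluded from PP, with ratings *d* points below the rest of the arm. Then:

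PP difference = -5 + *e* × *d*

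The chance that the PP lower limit exceeds -5 comes from the noncentral t distribution with noncentrality (*e* × *d*)/SE. The values of *e* and *d* are assumptions; the plan gives neither.

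| *e* | *d* | Test subjects (of 184) | PP difference | False success, subject level | False success, eye level |
|---|---|---|---|---|---|
| 0 | – | 0 | -5.0 | 5.0% | 5.0% |
| 2% | 15 | about 4 | -4.7 | 7.3% | 8.5% |
| 3% | 20 | about 6 | -4.4 | 10.4% | 13.6% |
| 5% | 10 | about 9 | -4.5 | 9.3% | 11.7% |
| 5% | 20 | about 9 | -4.0 | 15.8% | 23.1% |
| 5% | 30 | about 9 | -3.5 | 24.8% | 38.9% |

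Each rate is for one endpoint.

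**Power if both sets must pass.** Assume a true difference of 0, exclusions unrelated to outcome, 87% of those enrolled in PP (0.87 × 184 = 160) and 92% with at least one rating (0.92 × 184 = 169). By simulation, subject-level power per endpoint falls from about 94.2% for PP alone to 93.6% for both. A check with t limits gave 94.1% and 93.5%. At eye level it is 99.8% either way.

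**The case against.** The strongest objection is that the plan does not say discontinued subjects leave PP. Discontinuation is not a category in 8.6.4. The deviation there is failing to comply with assessment procedures, and sections 6.1.2 and 6.1.6 define a missed visit only for the 2-Week visit. Averaging non-missing values in the PP set (8.6.1.3) and analysing PP without imputation (8.6.7) both suggest that a PP subject may lack a visit. On that reading the 2-Week rating stays in and this route to bias closes. This stands as a limit on the claim. It also shows that 8.6.4 needs a sentence.

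A reader might infer from 3.2.3 that the plan removes subjects who do badly. It does not say so. Discontinuation for symptoms is optional, and schedule failure and lack of motivation, though mandatory grounds for discontinuation, are not PP exclusions. A reader might also take 8.6.7 to call analysis without imputation the conservative choice. It says only that imputation is not conservative. The fault lies in the step from there to PP alone.

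On size, a 30-point deficit is 30/13.9 = 2.2 SD, and nothing in the plan supports it or a 5% excess. Trial success also needs comfort, dryness and slit lamp findings all to pass, so a per-endpoint rate is not the trial's error rate.

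Finally, PP is a usual set for non-inferiority, the ITT result would be reported, and 8.6.1.1 defers detail to a separate SAP. None of this changes the decision rule in the text supplied, under which an ITT failure has no consequence.

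**Conclusion.** The point holds as a gap in the decision rule. Comfort and dryness are decided in PP alone, at least two PP exclusions can depend on tolerance, and the plan does not say what follows if ITT disagrees. The reason given in 8.6.7 does not support leaving observed ratings of randomised subjects out of the decision.

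The possible inflation is modest to large: about 7-9% in the mildest scenario, 10-14% in a middle one, and 25-39% in the severe one, against a nominal 5%. These ranges assume a true difference exactly at the margin, removal in excess on the Test arm, and removal that takes subjects out of PP after they have been rated. The severe case should not be read as the expected size, and the documents do not show that selective removal will occur. The case for a change is that the rule leaves this route open and closing it is cheap.

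**What to change.** 1. In 8.6.1.3, 8.6.1.4 and 8.6.8, state that each effectiveness endpoint succeeds only if the one-sided 95% lower limit exceeds -5 in both the PP set and the ITT set. Define the ITT analysis for this purpose as all randomised subjects with all available scheduled ratings. Keep the MCMC analysis as a supporting sensitivity analysis; it also addresses subjects who leave before giving any rating, whom the available-data analysis cannot include.
2. In 8.6.4, state whether a subject discontinued under 3.2.3 counts as having missed the later scheduled visits.
3. In 8.6.7, reword the argument so that the objection to imputation is not the reason given for using PP alone.

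Cost: wording in the protocol and the SAP before unmasking, with no new data and no larger sample. Under the stated assumptions, power per endpoint falls by about 0.6 points at subject level and hardly at all at eye level.
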